1.3. Aims

Aim 1. Develop an effective SCT education program for parents of infants with SCT identified by NBS.

- 1a. Determine the feasibility of implementing a SCT education program (SCTaware) that is appropriate for all parents, including those with low baseline knowledge and low health literacy. (Phase I)
- 1b. Determine if significantly more parents who receive SCTaware education have high SCT knowledge 6 months after receiving the education compared to baseline.

Hypotheses: SCTaware will require limited additional resources to implement compared to Ohio's current program and it will result in significantly more parents to have high SCT knowledge.

Approach: A comprehensive team will develop SCTaware education through iterative review and revision of the current in-person program. The time required to train the educator and to administer SCTaware to parents will be recorded. SCTaware will be feasible if educator training can be completed during administrative time and if SCTaware can be provided to parents within Ohio's existing appointment schedule (Phase I). The SCT Knowledge Assessment will measure parents' knowledge before, after, and 6 months post-SCTaware (Phase II).

Aim 2. Determine the barriers that prevent parents of infants with SCT from getting SCT testing.

- 2a. Determine the percentage of parents who obtain on-site SCT testing at time of SCTaware education. (Phase II)
- 2b. Determine the range of decisional conflict that parents may experience regarding SCT testing before and after receiving SCTaware education. (Phase II)

Hypotheses: Making on-site testing available will result in $\geq 50\%$ of parents who are educated to obtain testing. Parents will have decisional conflict about whether to obtain testing that will be reduced with SCTaware education.

Approach: Parents will self-report their SCT status before receiving education. The number of parents that obtain on-site testing will be recorded. We will use the Decisional Conflict Scale to measure parents' uncertainty about obtaining SCT testing before and after education. Parents who do not obtain testing will be asked to report their other testing barriers (e.g., cost, needle phobia, other).

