1.6. Expected Outcomes

This proposed work will provide important insights about how to effectively educate this underserved population about SCT, the SCT testing barriers that exist for parents of children with SCT, and if making on-site testing convenient increases SCT status awareness.

General Information

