Pilot Testing SCTaware Education Two new parents will be recruited to pilot test the SCTaware education, to have their SCTaware session video-taped and to complete the associated surveys, but additional parents will be recruited, if needed, so that at least one parent with low health literacy and baseline SCT knowledge pilot test the new program. The Team will the revise the SCTaware program again after reviewing their videos and surveys and pilot test the revised SCTaware program on two additional parents (at least one with low health literacy and baseline SCT knowledge). This process will continue iteratively until the Team agrees that the SCTaware program is finalized. The time required to deliver the SCTaware education during pilot testing will

be recorded. If it is not feasible to deliver SCTaware (i.e. SCTaware education cannot be delivered within the context of the current in-person SCT program), the current in-person SCT education will be tested in Phase II.

Parent stakeholders The NCH hemoglobinopathy team will help the Research Team identify the parent stakeholder of a child with SCT who has previously received the standard SCT education and the parent of a child with SCD who is currently followed by the NCH Hemoglobinopathy Team. These stakeholders will be compensated \$1000 each for their time to review the sessions and to provide their feedback, insights, and lived-experience that will inform the SCTAware education.

Phase II:

Study Design Phase II will be a six-month prospective study.

Recruitment Using the same recruitment strategy as in Phase I, we will recruit 128 parents.

Study Procedures Prior to receiving SCTaware, participants will self-report their SCT status and complete the demographic survey, SCTKA, State Trait Anxiety Index for Adults (STAID), and Decisional Conflict Scales (DCS).

Surveys	Before	After	Follow Up #1	Follow Up #2
	Day 1	Day 1	1 mo	≥6 mo
Demographics	x			
Self-reported SCT status	x		x	x
NVS	x			
SCTKA	x	x	x	x
DCS	x	x	x	
STNA		x		
STAID	x	x		
EES		x	x	x
ebook Survey			x	x

Table 2. Phase II Study Measures

SCTaware sessions will be timed. Participants will complete the DCS, EES, STNA, SCTKA, STAID immediately after their session and a research coordinator will contact parents by telephone one month and ≥6 months after their session to complete additional surveys (Table 2).

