SCT testing Barriers that prevent parents from obtaining SCT testing must be identified in order to increase SCT status awareness. Unresolved decisional conflict about whether or not to obtain SCT testing is a potential barrier, since the test results can have high-stakes for individuals who are identified as having SCT (e.g., being at risk for having a child with SCD). Decisional conflict is the psychological distress experienced when making a choice and it can lead to delayed and ineffective decision-making. Because decisional conflict can occur when individuals are uninformed about their options, effective education has the potential to reduce conflict and increase decision satisfaction. We will, therefore, use the Decisional Conflict Scale (DCS) to explore if parents experience decisional conflict about whether or not to obtain SCT testing and if SCTaware reduces this conflict (*Aim 2b*). Another potential barrier is that most parents of these children are African American and may not have access to a consistent provider who can order this testing.³⁸ To address this potential barrier, SCT testing will be available on-site, but not paid for, to participants after the educational program. SCT testing includes a CBC and a hemoglobin electrophoresis, and a paper order, signed by [name] (the PI and hematologist), will be provided to participants who wish to obtain this testing. Parents will be provided contact information for common insurance companies to determine if the testing will be covered but also informed of the estimated cost if not covered (~\$250). Finally, parents will be asked to report if they have other testing barriers (e.g., needle phobia, already aware of SCT status). [name] will review and interpret all test results and the SCT results will be mailed to tested parents. The research coordinator, using the teach-back method, will confirm test result receipt when parents are contacted to complete follow-up surveys.

Interim analyses will confirm that SCTaware does not result in more parents to have lower knowledge at 6 months. Several random sessions during Phase II will also be recorded and reviewed to confirm SCTaware education fidelity and that the teach-back method was used for the critical items, or if educator re-training is required.

6. Measures

Phase I:

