Demographic Survey Participants will self-report their age, SCT status, gender, race, ethnicity, primary language spoken, employment status, household income, and highest education level achieved.

NVS Participants will complete the NVS health literacy tool prior to their SCT education session. The NVS can be completed in less than three minutes and is highly sensitive for detecting adults with low health literacy.¹¹ Scores range from 0-6, and scores <4 will be considered low.

SCTKA Participants will complete the 8-item SCTKA (Table 2) before and after they receive education. This tool was used to quickly assess SCT knowledge during our preliminary study⁵ and to be understandable by those with low literacy levels. It was pilot tested in parents of children with SCT to ensure readability and seven of the items were previously published.¹² Scores <75% correct will be considered low.

STNA The SCTaware program in Phase II will make on-site SCT testing convenient to parents. To identify parents' testing needs and potential methods to use during SCTaware to promote parental learning and testing, parents will complete the STNA. It will ask parents about their knowledge of their SCT status and their intentions for obtaining SCT testing and it will be developed using the results of a qualitative study of pregnant women who identified the factors they found important when deciding whether or not to obtain SCT testing and will be pilot tested for readability on parents who come for standard in-person education and revised based on their feedback.¹³

EES Participants will complete a modified version of the education satisfaction survey that was used in the preliminary study.⁵ The EES will gauge parents' reported readiness and responsibility for learning about SCT, if the education they received met their learning goals, if they have the self-efficacy to apply their knowledge to make informed reproductive health decisions, and if they have (or plan to) notify family members or their communities about SCT and their SCT status. Participants will provide open-ended feedback and offer methods to improve and/or broaden the SCTaware program to increase SCT knowledge and awareness.

Phase II:

Demographic, NVS, SCTKA, STNA, and EES Same as in Phase I.

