Self-Reported SCT Status and Obtaining SCT testing Parents will self-report their SCT status multiple times during the study to determine if self-reported SCT status is reliable and accurate and impacts their decision to obtain testing. The percentage of parents who obtain on-site testing will be recorded to determine if on-site testing increases SCT status awareness and if tested parents can accurately recall their status ≥6 months after they were tested.

STAID (short form) Qualitative studies suggest that SCT education has the potential to reduce parental anxiety.⁶ The STAID short form is a 20-item sensitive and reliable measure of state anxiety and will be used to quantify parents' anxiety before and after receiving SCTaware education (Table 3).^{14,15}

DCS Participants will complete the 16-item validated tool to determine if decisional uncertainty is a SCT testing barrier for parents and if SCTaware increases parents' perception that they made an informed decision about whether to obtain testing. DCS has predictive validity over a range of decisions, and in studies of decision-supporting interventions, effect sizes ranged from 0.4-1.2.¹³⁻¹⁵

ebook Survey While most parents will have an electronic device, the non-interactive ebook content will be printed. Parents will be asked to report the type of device(s) they have since readability may differ by device, and to provide feedback on the content and format. They will also be asked to report how often they accessed the ebook since their in-person education to support their learning or to share information about SCT with their families and communities.

Time to Deliver SCTaware Education and Notifications Although health literacy-based methods can marginally increase the time to deliver information, in return, more learners may comprehend the information presented.¹⁶ We will compare the time to provide SCTaware education (Phase II) to Ohio's current in-person SCT education (Phase I). We anticipate that familiarity with SCTaware will reduce delivery time. The time to deliver parents' test results will also be recorded to determine if this testing can be included within the SCTaware program.

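### On-site testing uptake is used to judge whether status awareness rises; no baseline-to-follow-up awareness measure is defined, so the size of the gain could be overstated

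*Combined protocol and SAP*

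**What the plan says.** All references are to the combined protocol and SAP.

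- **Question.** Section 1.6 (Expected Outcomes) says the study will show "if making on-site testing convenient increases SCT status awareness".
- **Measure assigned to it.** Section 6, Phase II, paragraph on self-reported status and testing: "The percentage of parents who obtain on-site testing will be recorded to determine if on-site testing increases SCT status awareness". The same sentence goes on to a second purpose, "if tested parents can accurately recall their status", at 6 months or later.
- **Uptake hypothesis.** Section 1.3, Aim 2, expects on-site availability to lead at least 50% "of parents who are educated to obtain testing".
- **Baseline status.** Section 5f, Phase II: "Prior to receiving SCTaware, participants will self-report their SCT status and complete the demographic survey". Table 2 repeats self-reported status at 1 month and at 6 months or later.
- **Parents already aware.** Sections 2.4 and 2.5 do not exclude them. The SCT testing paragraph of section 5f has parents asked about "other testing barriers (e.g., needle phobia, already aware of SCT status".
- **Receipt.** The same paragraph has results mailed, and the coordinator "will confirm test result receipt when parents are contacted to complete follow-up surveys".
- **Testing needs survey (STNA).** "It will ask parents about their knowledge of their SCT status and their intentions for obtaining SCT testing" (section 6). Table 2 schedules it once in Phase II, after the education.
- **Analysis.** The Phase II text of section 10b covers Aim 1b (knowledge) only.

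**The concern.** An increase is a change from a starting point, and the percentage tested has no starting point. It differs from the gain in awareness in two ways. A tested parent who already knew their status, and was right, adds to uptake but not to awareness. A tested parent whose result never arrives also adds to uptake but has learned nothing.

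The plan schedules data that address both, but it does not say how they combine into an answer. The stated purposes of repeated self-report are its reliability, its accuracy and its bearing on the decision to test; change in awareness is not among them. As written, the section 1.6 conclusion would be read from uptake, and the same uptake figure fits gains of different size.

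**Working it through.** **The plan's own figures.** No figure is stated for awareness. The only sample-size calculation is for Aim 1b. With 50% discordant pairs and a 20-point difference, the McNemar formula gives (1.96 × √0.50 + 0.842 × √0.46)² / 0.20² = 95.7, or 96, close to the stated 98. That concerns knowledge and does not bear on this point. The figure that does is the hypothesised uptake of 50%: 0.50 × 128 = 64 parents tested.

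**Inputs**
- T = 0.50, share tested (section 1.3, hypothesis).
- N = 128 enrolled (section 10b).
- k = share who already know their status at baseline. It is not in the documents; 0.10 to 0.20 is assumed. The figure of over 80% unaware in section 1.1 is for people of childbearing age with the trait in general, not for these parents.
- a = share of tested parents who already knew. It follows from k and from who tests.
- r = share of newly tested parents who receive the result. It is not in the documents; r = 1 is assumed in the table.
- Baseline reports are taken as correct.

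**Formula.** Gain = T × (1 − a) × r.

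| Who tests | a | Gain, k = 0.10 | Gain, k = 0.20 |
|---|---|---|---|
| Aware parents do not test | 0 | 0.50 | 0.50 |
| Aware parents test at the common rate | k | 0.50 × 0.90 = 0.45 | 0.50 × 0.80 = 0.40 |
| All aware parents test | k / 0.50 | 0.50 − 0.10 = 0.40 | 0.50 − 0.20 = 0.30 |

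Reading the gain from uptake therefore overstates it by 0 to 20 points over this range. Incomplete receipt lowers it further: with a = 0 and an assumed r = 0.8, the gain is 0.50 × 0.8 = 0.40.

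**Which row fits the text.** Section 5f mentions being already aware among barriers to testing, and testing is not paid for by the study. Both favour the first row, where uptake and gain coincide if every result is received.

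**Precision of a measure in all 128 parents.** Half-width = 1.96 × √(p(1 − p)/128):
- p = 0.50: 8.7 points
- p = 0.40: 8.5 points
- p = 0.30: 7.9 points

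**Recall at 6 months or later.** Section 14, item 3, plans for 30% attrition. If 64 are tested, all unaware at baseline, and loss is unrelated to testing, 64 × 0.70 = 44.8 can be asked. If all of them recall correctly, confirmed recall is 44.8/128 = 35% with missing answers counted as not confirmed, and 64/128 = 50% with them counted as confirmed. This is a missing-data bound that any 6-month endpoint would have; it is not produced by the use of uptake. Receipt can also be documented at the 1-month contact, before most of that loss may have occurred.

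**The case against.** The strongest defence is that the plan is closer to an answer than one sentence suggests. The Aim 2 approach in section 1.3 pairs status reported before education with the count of parents tested. Section 6 relates reported status to the decision to test, which would show how many tested parents already claimed to know. Recall stands in the same sentence as uptake, and receipt is confirmed at follow-up. Section 2.5 excludes parents with previous trait education, with SCD, or with an affected child, so the share already aware may be below the assumed range. Uptake is also the proper endpoint for Aim 2a, and other secondary measures lack analysis text too.

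Most of this stands, and it rules out three stronger readings that a reader might infer:

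- *Awareness is not measured, or nothing links baseline status to testing.* Not supported: the data are scheduled and sections 1.3 and 6 make the link. What is missing is a defined combined measure.
- *Uptake could hide a negligible gain.* At 50% uptake, a gain near 5 points needs 80% of tested parents already aware and only half of the new results taking effect (0.50 × 0.20 × 0.50 = 0.05). Nothing in the documents supports either value.
- *The direction of the effect is in doubt.* It is not: the gain is positive in every row above, and section 1.1 reports that such parents did not obtain testing on their own.

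The defence does not supply the missing definition. Recall is limited to tested parents and has no baseline term, the STNA is given only once, and section 10b is silent on awareness. This is more than missing detail, because section 6 does name a measure for the question, and a better one can be built from data already scheduled.

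**Conclusion.** The point holds in a limited form. Uptake is assigned to a question about change, and no before-to-after awareness measure is defined, so the size of the gain would be read from uptake and could be overstated. At 50% uptake and full receipt, the true gain is 50 points on the reading closest to the text, 40–45 if aware parents test at the common rate, and 30–40 if all of them test. These figures rest on an assumed 10–20% already aware and on correct baseline reports.

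The 50% uptake hypothesis and primary Aim 1b are unaffected, and no decision rule depends on the awareness figure. The change should be made because the question is a stated expected outcome and the remedy is cheap.

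**What to change.** 1. Keep uptake among all educated parents as the Aim 2a measure.
2. In section 6, base the awareness conclusion on one main measure: the proportion, with a 95% CI, of all enrolled parents who reported at baseline that they did not know their status, were tested on-site, and were confirmed at follow-up to have received the result. Use the 1-month contact as well as the one at 6 months or later.
3. Report correct recall against the laboratory result at 6 months or later separately, with missing answers shown both as not confirmed and as confirmed.
4. Report the paired change in self-reported known status as supportive only.
5. State that Phase II has no comparator, so the change cannot be credited to on-site testing alone; education or testing elsewhere may contribute.

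**Cost.** This is analysis text, provided the status item separates not knowing from not having the trait; its wording is not shown and should be checked. The main measure relies on baseline self-report, which cannot be checked in untested parents, and a parent who wrongly claims to know their status would be left out although testing could inform them. Loss to follow-up lowers the confirmed proportion. For the supportive paired change, with about 90 parents followed (128 × 0.70 = 89.6) and 5% assumed to lose awareness, 1.96 × √((p_gain + p_lose − d²)/90) gives half-widths of 11.5 points at d = 0.30 and 12.2 at d = 0.50. Two parents of one child may both enrol (section 2.5, Note), but any allowance for this needs a family link that the documents do not say is recorded.

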Program Evaluation To evaluate the current program, 5 parents who attend NCH's in-person education session will be recruited to have their standard SCT education session video-taped, timed, and reviewed by the SCTaware Team which includes the includes: principal investigator, co-investigators, two parent stakeholders (a parent of a child with SCT and a parent of a child with SCD), and the SCT educator). Since >50% of parents had low health literacy and baseline knowledge in our preliminary study, we anticipate that this small sample will include at least 3 parents with low health literacy and 3 parents with low SCT knowledge, but if it does not, we will continue to enroll parents until at least 3 parents with these baseline characteristics are included in the initial program evaluation. Enrolled parents will self-report their SCT status, complete a demographic survey, and the sickle cell trait knowledge assessment (SCTKA) before the education. They will also complete the SCTKA, an SCT Testing Needs Assessment (STNA), and an Education Effectiveness Survey (EES) immediately after the education (Phase I. Study Measures).

The Team will review the participant videos and the SCTKA results to identify where the education was not clear or appropriate for those with low health literacy (i.e., too much medical jargon) or did not result in learners being able to correctly answer the corresponding SCTKA question. To determine if the existing print visual aids are suitable for those with low health literacy, multiple validated tools will be used. The Suitability Assessment of Materials (SAM) will assess the content, literacy demand, graphics, layout and typography, learning stimulation and motivation, and cultural appropriateness of the materials.⁷ The CDC's Clear Communication Index (CDCCI) will evaluate the clarity of the materials⁸ and the print and audio visual versions of the Agency for Healthcare Research and Quality's Patient Education Materials Assessment Tool (PEMAT) will evaluate the understandability and action-ability of the materials.⁹ Finally, the STNA, EES and parent stakeholder input will identify how to modify the education so that it applies Adult Learning Theory principles and promotes parents to want to learn about SCT and SCD, to obtain SCT testing, and to use their knowledge to make health decisions.

Phase I. Study Measures

Surveys	Before	After
	Day 1	Day 1
Demographics	x	
Self-reported SCT status	x	x
NVS	x	
SCTKA	x	x
EES		x
STNA		x

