Creating SCTaware Education Once the five sessions are evaluated, the SCT educator will receive additional health literacy- and Adult Learning Theory- based education. The educator will complete an in-depth experiential health literacy training and the online Always Teach-back! Toolkit interactive learning module. From the videos, the Team will create a plain language glossary for the SCT educator to use to reduce medical jargon during the education. The Team will provide specific feedback on strategies to make the education more understandable (e.g., open-ended questions, teach-back method, and Chunk and Check methods).¹⁰ The educator and a health literacy expert will role-play to increase the educators' comfort using these techniques. To ensure the educator consistently uses the health literacy strategies during all sessions, the TEAM will select the two SCTKA items that the educator will consistently use the teach-back method when educating parents about these items. Methods identified by stakeholders and on parents' STNA and EES surveys will be employed to further encourage parental learning. The time required to complete this additional educator training will be recorded. The Team will convert the print visual aids to be appropriate for those with low health literacy and also to be more interactive when they develop the SCTaware ebook that will be accessible on internet-enabled devices. The ebook will also include short videos, image hotspots, and quizzes to promote knowledge retention and to provide parents with a take-home tool to use to promote self-care in the Adapted Health Literacy Conceptual Model (Figure 2) and negotiate conversations about SCT with their family. The visual aids and ebook will be revised until they achieve pre-determined SAM, CDCCI, and PEMAT scores.

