7. Survey Completion- A research coordinator will read all survey items to participants and record their responses electronically. This format will be used because participants are only required to have functional verbal English and the NVS was validated using an interview format. This will also ensure that the method of survey completion is consistent in Phase II because the follow up surveys at 1 and 6 months will be over the telephone.

8. Study Compensation

Phase I: Participants will receive \$25 for completing Phase I.

Phase II: Participants will receive \$25, \$5, and \$10 for completing the initial, 1-month, and 6-month surveys, respectively.

9. Safety

a. Privacy

Participants' data will be de-identified to minimize the risk that participants' survey responses will be intercepted by a third party. The assessments will be completed electronically and stored in Redcap.

b. Data Storage

The survey results will be stored on a research drive that is maintained behind NCH secure firewall. The research data will be retained for 7 years after publication of the data, in accordance with standard research methods. After this time all collected data will be destroyed.

10. Data Management and Statistical Analysis

a. Data Monitoring

Study data will be collected, downloaded, and stored on RedCap. This database will only contain de-identified patient adherence data and will be linked by study ID number.

b. Statistical Methods and Analysis

Phase I: SCTaware will be deemed feasible if educator training and the time to deliver SCTaware can be delivered within the context of the current SCT program at NCH.

Phase II: During our preliminary study, ~40% of parents had high SCT knowledge prior to receiving education and 90% percent of parents achieved high SCT knowledge immediately after they received the current standard education program,⁵ however, it was unclear if this knowledge was sustained at 6 months because few parents completed the 6-month SCTKA. To determine if significantly more parents who receive SCTaware education have high SCT knowledge 6 months after receiving the education compared to baseline (Aim 1b, the primary aim for Phase II of the study), we will enroll 128 (n=98 evaluable) parents on Phase II of the study. This sample size was calculated using a two-sided, McNemar's test and has 80% power, with a 5% alpha, and assumes 30% attrition (Aim 1b).

Study Design	Knowledge Level at 6-month after SCTaware		

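### The 6-month SCTKA is read by telephone to parents who have the take-home ebook, with no closed-book instruction and no record of look-up, so open-book answers can bias the primary pre-post comparison upward

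*Combined protocol and SAP*

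**What the plan says.** - **Baseline.** The Phase II Study Procedures (Section 5f) put the first SCTKA on Day 1, ahead of the education: "Prior to receiving SCTaware, participants will self-report their SCT status and complete the demographic survey, SCTKA". Under Recruitment (Section 5b), parents are approached when they arrive for the in-person session.
- **Follow-up.** Section 7 (Survey Completion) states that "the follow up surveys at 1 and 6 months will be over the telephone".
- **Format.** Section 7 also says "A research coordinator will read all survey items to participants and record their responses electronically", and on that ground adds "This will also ensure that the method of survey completion is consistent in Phase II".
- **Material at home.** Under Creating SCTaware Education, the ebook is developed from the session's visual aids and includes "quizzes to promote knowledge retention and to provide parents with a take-home tool". The ebook Survey paragraph in Section 6 adds that "the non-interactive ebook content will be printed".
- **Link to the test.** In the Phase I Program Evaluation, the team looks for places where the teaching "did not result in learners being able to correctly answer the corresponding SCTKA question".
- **Same contact.** Table 2 schedules both the SCTKA and the ebook survey at 1 month and at 6 months or later. No order within the call is given. The ebook survey asks how often the ebook was opened since the session, not whether it was open during the test.
- **Endpoint and test.** Section 6 scores the 8-item SCTKA as low below 75% correct. Section 10b compares high knowledge at 6 months with baseline by a two-sided McNemar test at 5% alpha, with 98 evaluable parents.

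**The concern.** The two measurements being compared differ in what the parent has to hand. At baseline no SCTaware material has been given out. At 6 months the parent is out of the coordinator's sight and has a take-home resource covering what was taught. Consulting accurate material during the call can raise the 6-month score and cannot touch the baseline score.

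Section 10b presents the open question as whether knowledge lasts to 6 months. An answer read from the ebook does not show that. There is no control arm in which the same artefact would appear and cancel. The cut-off makes the endpoint sensitive: 75% of 8 items is 6, so a parent who knows 5 needs only one looked-up answer to change category.

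**Working it through.** **1. The plan's own figure.** Section 10b gives 35% low-to-high and 15% high-to-low, so the discordant share is s = 0.50, the difference is d = 0.20 and the odds ratio is 0.35/0.15 = 2.33.

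n = (1.960 + 0.842)² × s/d² = 7.849 × 0.50/0.04 = 98.1

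This reproduces the stated 98. Power at 98 is 80.9% by the normal approximation and 78.0% by the exact McNemar test. The sample size is not in question here.

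**2. Model for look-up.** Let f be the share of truly low parents at 6 months who are scored high because they consulted material. The documents give no value, so f is an assumption shown over a range. The null is also assumed: 45% high at both times, with true discordance split equally as b in each direction (b = 0.25 for discordance 0.50, b = 0.15 for 0.30). The observed cells become:

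- high-to-low: HL = b(1 − f)
- low-to-high: LH = b + f(0.55 − b)
- observed high at 6 months: 0.45 + 0.55f

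**3. Chance of a significant result in favour of SCTaware.** With d = LH − HL and s = LH + HL,

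P = Φ[(d√98 − 1.960√s)/√(s − d²)]

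Example with b = 0.25 and f = 0.10: HL = 0.225, LH = 0.280, d = 0.055, s = 0.505. Then P = Φ[(0.544 − 1.393)/0.7085] = Φ(−1.20), about 11.6%. Summing over all outcomes of the asymptotic test gives 11.5%. The table uses that summation.

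| f (assumed) | Observed high at 6 months | Discordance 0.50 | Discordance 0.30 |
|---|---|---|---|
| 0 | 45.0% | 2.5% | 2.6% |
| 5% | 47.8% | 5.7% | 7.2% |
| 10% | 50.5% | 11.5% | 15.8% |
| 20% | 56.0% | 33.1% | 45.8% |

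The exact McNemar test gives lower figures with the same pattern: 9.2% and 11.5% at f = 10%, and 28.7% and 38.6% at f = 20%.

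**4. What f means.** f counts parents whose category changes, not parents who open the ebook. Some who look up an answer will still score below 6 of 8, so the look-up rate among truly low parents must be at least f.

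**5. Scale against the planned effect.** Producing the planned 65% with no real gain would need 0.55f = 0.20, that is f of about 36%. If instead the planned gain is real, f = 10% moves the observed rate from 65% to 0.65 + 0.10 × 0.35 = 68.5%, which overstates a 20-point gain by 3.5 points.

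**The case against.** The strongest reply is that no look-up has been shown. The coordinator reads a short test aloud and records answers live. Section 8 pays for completing surveys, not for scoring well. Section 11 plans staff training in survey administration, and a closed-book instruction may be a call-script detail that a protocol need not carry. All of this is fair. It limits the point to a risk of unknown size, but no passage confirms that the script covers it.

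A second reply is that the ebook belongs to the intervention. This stands in full: a parent who learned from it between contacts has the knowledge that the trial aims to produce. It does not cover answers looked up during the test.

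A third is that an exact null is extreme, since Section 10b reports 90% high immediately after the standard education against about 40% before. That is reasonable, though 6-month retention is what the plan says is unknown. With a real gain, the consequence is an overstated effect instead of a false positive.

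Some stronger readings are tempting but unsupported:

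- **Section 7's consistency statement is false.** It refers to the coordinator-read format, which is the same at every time point, and Section 7 openly says that follow-up is by telephone. It simply does not address access to materials.
- **Telephone mode itself biases upward.** The documents establish no direction for mode.
- **The ebook contains the SCTKA items.** That it covers the tested content is a fair inference from how the education is developed. No passage says that it reproduces the questions.

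**Conclusion.** The point holds as a preventable risk to the primary endpoint. Baseline and 6-month scores are taken under different access to the taught content, nothing asks for closed-book answers, and nothing recorded would show afterwards whether look-up occurred. Look-up during the call works in one direction only, and the single-group design cannot absorb it.

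A reader might infer that the primary comparison is biased. The documents support only that it can be. The false-positive figures rest on an assumed f, an assumed null of 45% at both times, 98 pairs and discordance of 0.30 to 0.50. On those terms, even f = 5% takes the chance of a false finding of benefit from about 2.5% to 6-7%. The figures should not be read as the effect of 5%, 10% or 20% of parents using the ebook.

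**What to change.** In Section 7:

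1. Add one scripted line at the start of each telephone SCTKA asking the parent to put the ebook or printout away and answer from memory.
2. State that the SCTKA is given before the ebook survey, so that the call itself does not prompt the parent to open the ebook.
3. Record one yes/no item on whether any material was used during the SCTKA.

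In Section 10b, pre-specify a sensitivity analysis of the primary comparison that excludes parents who answer yes and, separately, counts them as low at 6 months. The second version is a worst-case lower bound, because some of those parents would have scored high unaided, and it should be labelled as such.

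The cost is one script line, one data item and one extra analysis, with no change to sample size or staffing. Self-reported use is likely to be under-reported, so the item limits the problem without removing it. It has to be in place before the calls, since it cannot be collected reliably afterwards.
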